4.4 Early Withdrawal of Subjects

4.4.1 When and How to Withdraw Subjects

A subject may be withdrawn from the study prior to expected completion for the following reasons:

- Participant or participant's parent(s) withdraw consent
- Participant fails to adhere to protocol requirements (no show to 3 appointments)

CONFIDENTIAL

This material is the property of the University of Minnesota. Do not disclose or use except as authorized in writing by the study sponsor

- Participant experiences adverse side effects to the fluoxetine that are intolerable to the adolescent or the parent.
- Participant experiences a significant worsening in symptoms: the participant will be evaluated by an independent safety monitor if at any time any of the following occur: 1) a suicide attempt, 2) serious suicidal ideation (with a plan and/or intent) and refusal to contract for safety, 3) psychiatric hospitalization, 4) possible need for psychiatric hospitalization, or 5) significant worsening of depressive or other clinical symptoms (CDRS-R > 76 or CGI improvement score > 5). Adolescents will be removed from the study immediately following review if the independent safety monitor deems that the patient requires treatment outside of study protocols or if the treatment provided in the study is contraindicated.

If a subject exits the study for any reason, the participant will be provided with referrals to receive treatment out of the protocol.

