4.4.2 Data Collection and Follow-up for Withdrawn Subjects

In the event of subject withdrawal from the treatment, we will ask permission to contact the family to continue to complete the study evaluations. Subjects will be determined lost to follow-up if they do not respond to 3 phone calls to their primary number.

5 Study Drug

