Assessments. Adolescents will enter continuation treatment at week 16. Assessments will be conducted at week 24 and 32. The week 32 evaluation is already funded through the K23 study.

7 Statistical Plan

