- Hypotheses 5 & 6: (1) Primary analyses will examine within-subject change scores in CDRS, C-SSRS and CGAS over the course of acute and continuation treatment using repeated measures analysis of variance (ANOVA). Linear regression and analysis of covariance (ANCOVA) adjusting for pre-treatment scores will also be used to analyze changes in adolescents' outcomes. The magnitudes of changes in outcomes variables over time will be assessed using the paired t-test or Wilcoxon signed-rank test for continuous variables. Mixed-effects regression models will also be employed to compare CDRS, C-SSRS, and CGAS scores over multiple time points in order to obtain information on specific patterns of change over time. (2) Secondary analyses comparing within-subjects change scores across treatment groups on self-report measures of depression (BDI-II) and functioning (CBQ, SAS-SR) will be conducted using two-sample t-test, Wilcoxon rank sum test, and linear regression analysis. Hierarchical linear modeling (HLM) will also be conducted to compare scores over multiple time points within each treatment group. (3) Recovery will be defined as an absence of depression symptoms on the KSADS-PL for at least 8 weeks. Relapse will be defined as the reemergence of 5 or more symptoms of depression on the KSADS-PL. The percentage of adolescents who meet recovery criteria, and associated 95% confidence interval will be calculated. The percentage of adolescents who meet relapse criteria, and associated 95% confidence interval will be calculated. For those with a relapse, the mean (SD) time from recovery to relapse will be calculated.

Exploratory Analyses: Exploratory analyses will be conducted to determine whether comorbid psychiatric disorders, baseline severity of depression, and different forms of functioning (CBQ, SAS-SR, CGAS) predict or moderate positive or negative treatment outcomes. Potential predictors and moderators will be used to refine the personalized treatment strategy that will be tested in the subsequent R01.

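### Relapse is defined by the K-SADS-PL alone, so an adolescent removed or hospitalized for depressive worsening with no later interview cannot be counted, and the relapse percentage may be understated

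*Combined protocol and SAP*

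**What the plan says.** Section 7.2, item 3 under Hypotheses 5 & 6, gives two definitions. For recovery: "Recovery will be defined as an absence of depression symptoms on the KSADS-PL for at least 8 weeks". For relapse: "Relapse will be defined as the reemergence of 5 or more symptoms of depression on the KSADS-PL". It then commits to a summary: "The percentage of adolescents who meet relapse criteria, and associated 95% confidence interval will be calculated". For those who relapse, it adds the mean time from recovery to relapse. No denominator is named for the relapse percentage. Section 7.2 places all analyses on the intent-to-treat sample.

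Section 3.1 lists the K-SADS-PL in the independent evaluators' battery. On timing, 3.1 and Section 6 both say: "Assessments will be conducted at week 24 and 32". Section 8.4 names the measures used at therapy sessions as the BDI-II, CGI-I and CGI-S, with a suicidality assessment. The K-SADS-PL is not among them.

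Sections 4.4.1 and 8.4 send certain events to an independent safety monitor. The list includes a suicide attempt, "3) psychiatric hospitalization, 4) possible need for psychiatric hospitalization", and significant worsening (CDRS-R above 76 or CGI improvement score above 5). Removal depends on that review: "Adolescents will be removed from the study immediately following review if the independent safety monitor deems" that outside treatment is required or that study treatment is contraindicated. For withdrawn subjects, 4.4.2 says "we will ask permission to contact the family to continue to complete the study evaluations".

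**The concern.** The relapse outcome and the safety route do not meet. The events most likely to be severe depressive relapses are reviewed and recorded in one place, while relapse is scored in another, on an instrument scheduled twice during continuation. Consider an adolescent who has recovered, worsens between weeks 24 and 32, is removed after review, and whose family declines further evaluation. That adolescent has no K-SADS-PL on which relapse could be found.

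Such a loss would be related to outcome, and it can only push the percentage down. Section 1.1 names avoiding relapse as a goal of continuation treatment, and Hypothesis 5 is about sustained response. A relapse percentage that can omit its most severe cases would make the strategy look more protective than it was. The printed confidence interval would not show this, because it reflects sampling error only.

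**Working it through.** **The plan's own figure.** There is nothing to reproduce. Section 7.1 chooses 30 adolescents for feasibility and acceptability, with no power calculation and no assumed relapse rate.

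**Inputs**
- N = 30 (7.1).
- T = number who truly relapse. No value is given for continuation treatment. As an illustrative range I use the 25-50% that 1.1 reports for relapse after acute treatment studies: 25% of 30 is 7.5, rounded to 8, and 50% of 30 is 15.
- m = number of relapsers removed and never re-assessed. The documents give no rate of removal, hospitalization or refusal, so m is an assumption, varied from 0 to 5.

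**Formulas**
- Kept in the denominator as not relapsed: (T − m)/30. The loss is m/30, or 3.3 points per case.
- Dropped from the denominator: (T − m)/(30 − m).

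| m | T = 8, kept (exact 95% CI) | T = 8, dropped | T = 15, kept (exact 95% CI) | T = 15, dropped |
|---|---|---|---|---|
| 0 | 26.7% (12.3-45.9) | 26.7% | 50.0% (31.3-68.7) | 50.0% |
| 1 | 23.3% (9.9-42.3) | 24.1% | 46.7% (28.3-65.7) | 48.3% |
| 2 | 20.0% (7.7-38.6) | 21.4% | 43.3% (25.5-62.6) | 46.4% |
| 3 | 16.7% (5.6-34.7) | 18.5% | 40.0% (22.7-59.4) | 44.4% |
| 5 | 10.0% (2.1-26.5) | 12.0% | 33.3% (17.3-52.8) | 40.0% |

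**Reading the table**
- The direction is downward under either denominator.
- With 1 to 5 missed cases kept in the denominator, the loss runs from 3.3 to 16.7 points (5/30).
- With m = 0, because every removed adolescent is re-assessed and the relapse is recorded, the loss is zero.
- At m = 0 the interval is 33.6 points wide for T = 8 (45.9 − 12.3) and 37.4 points wide for T = 15 (68.7 − 31.3). One or two missed cases therefore sit well inside sampling error.

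**If the denominator is those who recovered.** Let R be the number who met the recovery criterion. Each missed case then costs 1/R. Because R cannot exceed 30, this is at least 3.3 points per case. R is not predictable from the documents.

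**The case against.** **Symptoms can be dated between visits.** Section 7.2 does not confine relapse to symptoms present on the visit day. An 8-week symptom-free period and a time from recovery to relapse both imply dating between visits. On that reading, an episode that led to hospitalization is picked up at the next interview. This stands, but only where the next interview takes place, and the plan does not state the reading.

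**Follow-up is partly provided for.** Hospitalization or a suicide attempt triggers review, not automatic removal, and an adolescent who stays keeps the scheduled K-SADS-PL. Families of withdrawn subjects are asked to continue evaluations, and the analysis is by intention to treat. This also stands in part. But 4.4.2 only asks permission, and it treats three unanswered calls as loss to follow-up. It speaks of withdrawal from treatment, whereas 4.4.1 speaks of removal from the study, so its coverage of safety removals is unclear. Intention to treat keeps an adolescent in the analysis set but does not supply a missing interview.

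**Not every such event is a relapse.** Partial responders are eligible and some may never meet the recovery criterion. The triggers also include suicidality and other clinical symptoms. Counting every removal as relapse could overstate the rate. This stands, and it is why the K-SADS-PL definition should be kept.

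**Relapse is a minor outcome here.** It is neither the primary outcome (3.2) nor a listed secondary one (3.3), and 7.1 disclaims any efficacy evaluation. Severe failures also appear in dropout, in the C-SSRS and in serious adverse event reports. This limits the importance of the point. It does not repair the percentage that 7.2 commits to reporting.

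**Conclusion.** The point holds as a gap in the definition. As written, the plan can leave a severe relapser out of the numerator, and any such loss is downward. The cost is 3.3 points per missed case in a denominator of 30, and zero if all are re-assessed and the relapse is recorded.

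A reader might infer more: that the percentage is in fact understated, or that some definite share of relapses will be missed. The documents do not support either. They give no removal, hospitalization or refusal rate, removal is conditional on review, and continued evaluation is sought. The 25-50% range is background from acute treatment studies. Section 1.1 also says that continuation treatment is associated with a lower risk, so the range serves here only to illustrate.

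This is an inexpensive improvement to a descriptive measure in a 30-person open-label pilot. It does not threaten the feasibility aims.

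**What to change.** In 7.2, item 3:

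1. Keep the K-SADS-PL definition of relapse, and state that it counts symptoms at any time since the last assessment.
2. Fix the denominator as adolescents who met the recovery criterion, and report how many of them have no later K-SADS-PL.
3. Beside that figure, pre-specify a sensitivity relapse percentage in the same denominator. It would also count removal from the study, psychiatric hospitalization or suicide attempt when recorded as due to depressive worsening, dated at the event.
4. Report the same events in adolescents who never recovered separately, as worsening and not as relapse.

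The cost is slightly more than a wording change. The safety monitor is now asked about the need for outside treatment and whether study treatment is contraindicated, not about the cause of the event, so one attribution item must be added to the existing safety-review record. The sensitivity figure is a composite and may be less favourable than the K-SADS-PL figure. No clinical management rule changes.

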1.1 Background

Adolescent depression is a prevalent and debilitating disorder that places youth at risk for suicidality, other psychiatric diagnoses, and significant psychosocial impairment both during adolescence and into adulthood.^{1,2} Research on the treatment of adolescent depression has dramatically increased over the past two decades. Two psychotherapies meet the American Psychological Association's criteria for "well-established" treatments (interpersonal psychotherapy and cognitive behavioral therapy).³ Fluoxetine, paroxetine, sertraline, and escitalopram also have demonstrated efficacy as pharmacological treatments.⁴⁻⁸ While the progress in this area has been substantial, the overwhelming majority of treatment studies have focused on the acute phase of treatment, that is, the phase of treatment focused on initial clinical response and remission of symptoms.⁹ However, among the acute treatment studies that have reported long-term follow-up data, 25-50% of the adolescents in these studies experienced a depressive relapse following the completion of treatment.¹⁰⁻¹³

The American Academy of Child and Adolescent Psychiatry Practice Parameter for the treatment of depression recommends providing continuation treatment following the symptom remission achieved during the acute phase of treatment.¹⁴ The goals of continuation treatment are to consolidate the acute phase treatment response and avoid relapse. Research on continuation phase treatment for adolescent depression is extremely limited, and as a consequence, this Practice Parameter was based primarily on adult treatment studies and clinical consensus.¹⁴ The handful of studies with adolescents that have examined postacute treatment have found that continuation treatment is associated with a decreased risk of relapse,^{11,15,16} and can facilitate further symptom reduction in adolescents who were partial responders to acute phase treatment.^{11,17}

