4.1 Inclusion Criteria

- Male and female adolescents ages 12-18
- Completed acute phase treatment and showed at least a partial response to treatment (CGI-I of minimally improved or better ($CGI-I \leq 3$)).⁵⁰

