7.2 Statistical Methods

All statistical analyses will be conducted on the intent-to-treat sample.

- Hypothesis 1: Among families in the acute phase study who are eligible to participate in continuation treatment, the percentage of adolescents and parents

CONFIDENTIAL

who consent to participate in the continuation treatment, and associated 95% confidence intervals will be calculated.

- Hypothesis 2: The mean/median (depending on the distribution) number and proportion of sessions attended by adolescents, as well as the associated 95% confidence intervals, will be calculated. The proportion of adolescents dropping out of treatment prematurely, and the associated 95% confidence interval, will be calculated.
- Hypothesis 3: An overall mean treatment satisfaction rating, and associated 95% confidence interval, will be calculated based on adolescents' and parents' responses on the CSQ-8.
- Hypothesis 4: An overall mean treatment satisfaction rating and the associated 95% confidence interval will be calculated based on clinicians' response on the clinician satisfaction measure.

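### Time to relapse is averaged over relapsers only, so the week 32 window bounds it and it says little about how long recovery lasts; the relapse percentage, most naturally read over all 30 enrolled, is not the risk after recovery

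*Combined protocol and SAP*

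**What the plan says.** Section 7.2, item (3) under Hypotheses 5 and 6, defines two states on the K-SADS-PL. For recovery: "Recovery will be defined as an absence of depression symptoms on the KSADS-PL for at least 8 weeks". For relapse: "Relapse will be defined as the reemergence of 5 or more symptoms of depression on the KSADS-PL". Two summaries of relapse follow. The first is a proportion: "The percentage of adolescents who meet relapse criteria, and associated 95% confidence interval will be calculated". The second is a time: "For those with a relapse, the mean (SD) time from recovery to relapse will be calculated". The percentage meeting recovery is also planned, with a 95% confidence interval.

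The same section opens with a blanket rule: "All statistical analyses will be conducted on the intent-to-treat sample". Section 7.1 sets that sample at 30. Section 4.1 admits partial as well as full responders: "Completed acute phase treatment and showed at least a partial response to treatment". Section 6 (Assessments) fixes the schedule: "Adolescents will enter continuation treatment at week 16. Assessments will be conducted at week 24 and 32".

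The plan contains no censoring rule, Kaplan-Meier estimate, cumulative incidence or person-time rate. It also does not say whether recovery is dated at the start or the end of the 8 symptom-free weeks, or whether relapse is dated by visit or by recall.

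**The concern.** An average over relapsers alone discards the adolescents who hold their recovery, and they carry most of the information about how long recovery lasts. When every observed relapse must fall inside a short fixed window, the average is confined to that window and moves little with the underlying relapse rate.

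The percentage has a different problem. Section 4.1 admits partial responders, who may never reach 8 weeks without symptoms. If they stay in the denominator but cannot relapse from recovery, the figure mixes how many recovered with how many of those relapsed.

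These are the plan's only summaries of relapse, and Section 1.1 names avoiding relapse as a goal of continuation treatment. A reader planning the follow-on trial could take the mean as the duration of recovery and the percentage as the risk after recovery.

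**Working it through.** The plan gives no expected recovery rate, relapse rate or time to relapse, so it has no figure to reproduce. The calculations below are illustrations with labelled assumptions.

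**Inputs from the documents.** Planned intent-to-treat sample 30 (Section 7.1). Entry at week 16, assessments at weeks 24 and 32 (Sections 3.1 and 6). Recovery needs at least 8 symptom-free weeks (Section 7.2). Section 1.1 reports that "25-50% of the adolescents in these studies experienced a depressive relapse following the completion of treatment", with no time horizon.

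**Assumptions.** The 25% and 50% figures apply over the 16 weeks from week 16 to week 32; the hazard is constant; counts of recovered and relapsed adolescents are invented.

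**1. Relapser-only mean.** With relapse proportion q over 16 weeks, λ = −ln(1−q)/16. The mean time among those relapsing within W weeks is 1/λ − W·exp(−λW)/(1−exp(−λW)).

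- q = 0.25: λ = 0.01798 and 1/λ = 55.6. For W = 16: 55.62 − 16 × 0.75/0.25 = 7.62 weeks (SD 4.61).
- q = 0.50: λ = 0.04332 and 1/λ = 23.1. For W = 16: 23.08 − 16 × 0.50/0.50 = 7.08 weeks (SD 4.56).
- The hazards differ by a factor of ln(0.50)/ln(0.75) = 2.41, yet the means differ by about 0.5 week. With 15 recovered, 15 × 0.25 = 3.75 and 15 × 0.50 = 7.5 relapses are expected. The standard errors are about 4.61/√4 = 2.3 and 4.56/√8 = 1.6 weeks.
- If recovery is first met at week 24, W = 8 and the means are 3.90 and 3.77 weeks.

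Over a wider set of assumed rates (25% or 50% relapse by 8, 16, 26 or 52 weeks), the relapser-only mean is 3.5 to 4.0 weeks for W = 8, 6.2 to 7.9 for W = 16 and 8.1 to 11.7 for W = 24. The untruncated mean ranges from 11.5 to 181 weeks. The 24-week window allows for symptom-free time in the acute phase counting toward recovery.

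**2. Dating.** Suppose recovery is met at week 16 and relapse is dated at the visit that detects it. The share of relapsers found at week 24 is (1−√(1−q))/q = 0.536 or 0.586. The mean is then 8 × 0.536 + 16 × 0.464 = 11.7, or 8 × 0.586 + 16 × 0.414 = 11.3 weeks. With continuous dating, but recovery dated at the start of the 8 weeks, 8 weeks are added: 15.6 and 15.1. The choice of convention moves the result far more than doubling the relapse proportion does.

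**3. Denominator.** Let R be the number who recovered and x the number who relapsed. If every relapse follows a recovery, x/30 = (x/R) × (R/30). With x = 4 the all-enrolled figure is always 4/30 = 13.3% (exact 95% CI 3.8–30.7). Among the recovered:

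| R | x/R | Exact 95% CI |
|---|---|---|
| 10 | 40.0% | 12.2–73.8 |
| 15 | 26.7% | 7.8–55.1 |
| 20 | 20.0% | 5.7–43.7 |
| 25 | 16.0% | 4.5–36.1 |

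At R = 30 the two figures coincide.

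**4. Why x/R alone is not enough.** With the same hazards, the relapse-free proportion at week 32 is 75% or 50% for recovery at week 16, but √0.75 = 86.6% or √0.50 = 70.7% for recovery at week 24. A simple proportion among the recovered therefore depends on when they recovered. Someone who recovers near week 32 counts as relapse-free with almost no time at risk.

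**The case against.** A reader might infer that the plan fixes the relapse denominator at all 30 and that the percentage necessarily understates risk. The documents support neither outright. The relapse sentence names no denominator, and Section 7.2 departs from its own blanket rule elsewhere: Hypothesis 1 uses eligible families and Hypothesis 4 uses clinicians. All 30 is the likelier reading, not a stated one. The relapse definition does not require prior recovery either; only the planned time from recovery to relapse implies it. Without that requirement the bias can reverse. With 4 relapses, 2 of them after recovery, and 20 recovered (assumed), 4/30 = 13.3% exceeds 2/20 = 10%.

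The share of all enrolled adolescents who relapse is also a legitimate quantity. If relapse does require recovery, the counts behind the two planned percentages give x/R and its exact interval in one line.

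On timing, the constant-hazard illustration varies the rate and not the pattern. If all relapses fell within 4 weeks, the mean could not exceed 4, so it does say something about when observed relapses occur. It is also openly labelled as covering relapsers only.

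These points limit the claim about the percentage. They do not rescue the mean as a measure of how long recovery lasts, because it still omits everyone who stayed well.

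**Conclusion.** The concern about the mean rests on explicit text: it is restricted to relapsers, no censoring method is planned, and follow-up ends at week 32. The size of the effect (7.6 versus 7.1 weeks for 25% versus 50% relapse) depends on the assumed constant hazard and 16-week horizon. The exclusion of those still well and the bound set by the window do not.

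The concern about the percentage is conditional. Over all 30, and if relapse requires recovery, it equals the risk after recovery multiplied by R/30, and understates that risk whenever R is below 30. The plan states neither condition, and the counts shown are assumed.

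Severity is minor. The item is descriptive, relapse is not among the endpoints in Sections 3.2 and 3.3, and Section 7.1 disclaims any aim to evaluate efficacy. A reader might infer that Hypothesis 5 on sustained response stands or falls on these summaries. It does not: Section 7.2 also gives it repeated-measures and mixed-model analyses. The sample size and the primary feasibility endpoint are unaffected.

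**What to change.** Amend item (3) of Section 7.2 as follows.

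- Replace, or at least supplement, the relapser-only mean with a time-to-event estimate from recovery among adolescents who met the recovery definition. Use Kaplan-Meier or an interval-censored method, censor at the last K-SADS-PL, and show numbers at risk. This is the main change, because a week 32 relapse-free proportion is only the complement of the relapse proportion and credits late recoverers with little time at risk.
- Report relapse among the recovered (x/R) with an exact 95% confidence interval, beside the intent-to-treat percentage, with both denominators named.
- List return to 5 or more symptoms without prior recovery separately.
- State one dating rule for recovery and one for relapse.

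The cost is SAP wording; the K-SADS-PL data are the same and no visit is added. The interval is wider (for example 7.8–55.1% for 4/15 against 3.8–30.7% for 4/30, assumed counts), and with two continuation visits the curve will be coarse.

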3.1 General Design

Adolescents will receive 16 weeks of continuation treatment. They will be treated by the same clinicians who provided their acute phase treatment. The personalized continuation treatment plan is illustrated below.

Continuation IPT-A. The goal of IPT-A²⁰ is to decrease depressive symptoms by focusing on current interpersonal difficulties and helping the individual improve his or her relationships and interpersonal interactions. This is accomplished through review of the

[figure not shown]
[figure not shown]
adolescent's significant relationships which leads to the identification of the interpersonal problem areas on which to focus the treatment, development of communication and interpersonal problem solving skills, and role-playing. During the Continuation IPT-A sessions, the therapist will continue to emphasize the interpersonal strategies that were learned and practiced during the acute phase, and address any current interpersonal problems before they result in a recurrence of depressive symptoms. Adolescents who have responded to acute phase treatment (CGI-I = much improved or very much improved) will attend 4 biweekly IPT-A sessions followed by 2 monthly sessions. Adolescents who showed a partial response to acute phase treatment (CGI-I = minimally improved) will attend 8 weekly IPT-A sessions followed by 2 monthly sessions.

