5.2 Treatment Regimen

Adolescents who received fluoxetine during the acute phase and were responders (CGI-I = much improved or very much improved (CGI-I = 1 or 2)) will continue their acute phase dosing regimen and will meet with the psychiatrist on a monthly basis.

Adolescents who received fluoxetine during the acute phase and were partial responders (CGI-I = minimally improved (CGI-I = 3)) will enter the continuation phase on 40mg fluoxetine, and will have their dose increased to 60mg. Partial responders will meet with the psychiatrist biweekly for the first 2 months and monthly for the second 2 months. Adolescents who received only IPT-A during acute phase and were partial responders (CGI-I = minimally improved (CGI-I = 3)) will begin treatment with fluoxetine during the continuation phase, in addition to continuing their IPT-A treatment. The dosage schedule will be 10mg per day for the first week and 20mg per day for the following 5 weeks. If no treatment response is observed by the 6th week, the dosage can be increased to 40mg per day. Pharmacotherapy sessions will be scheduled weekly for the first 4 weeks and biweekly thereafter. Pharmacotherapy sessions will include assessment of vital signs, adverse effects, safety, and symptomatic response.

CONFIDENTIAL

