5.3 Method for Assigning Subjects to Treatment Groups

There is no randomization in this study. Assignment to treatment groups is described above (based on CGI-I score).

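### Continuation treatment follows from acute treatment and response, so section 7.2 can study predictors of outcome but not moderators of the continuation-treatment effect

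*Combined protocol and SAP*

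**What the plan says.** The exploratory paragraph of section 7.2 will examine whether comorbid disorders, baseline depression severity and functioning (CBQ, SAS-SR, CGAS) "predict or moderate positive or negative treatment outcomes". It then gives the result a use: "Potential predictors and moderators will be used to refine the personalized treatment strategy that will be tested in the subsequent R01". It names no model, no treatment contrast whose size is thought to vary, and no limit on interpretation.

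On allocation, section 5.3 says "There is no randomization in this study" and that groups follow the CGI-I score. Section 5.2 sets the drug plan:

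- Fluoxetine responders "will continue their acute phase dosing regimen and will meet with the psychiatrist on a monthly basis".
- Fluoxetine partial responders "will enter the continuation phase on 40mg fluoxetine, and will have their dose increased to 60mg".
- Partial responders to IPT-A alone "will begin treatment with fluoxetine during the continuation phase, in addition to continuing their IPT-A treatment".
- No drug is listed for responders to IPT-A alone.

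Section 3.1 sets the psychotherapy plan by response. Responders "will attend 4 biweekly IPT-A sessions followed by 2 monthly sessions"; partial responders have eight weekly sessions and then two monthly ones.

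Two other statements bear on how the paragraph should be read. Aim 3 in section 2 calls this work exploratory and hypothesis-generating. Section 7.1 cautions against over-reading pilot data and says that the study does not set out to evaluate efficacy.

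**The concern.** A predictor is related to outcome. A moderator is a factor across which the difference between two treatments changes. To see moderation, comparable patients must have received different treatments. Here two adolescents with the same acute treatment and the same response category enter the same continuation plan, so no such comparison exists within any category.

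The plan's label matters because the result has a stated destination. A factor that only marks poorer prognosis among partial responders could be reported as a moderator. It could then enter the next strategy as a reason to choose one continuation treatment over another.

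**Working it through.** There is no figure in the plan to reproduce. The sample of 30 in section 7.1 was chosen on feasibility grounds, without alpha, power, effect size or SD. The question is whether the quantity is identified, so the check starts there.

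**Step 1. Write the assignment rule as variables.** Let F = 1 if fluoxetine was given in the acute phase and P = 1 for a partial responder (sections 3.1 and 5.2).

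| F | P | IPT-A sessions | Fluoxetine at entry |
|---|---|---|---|
| 0 | 0 | 4 + 2 = 6 | none listed |
| 0 | 1 | 8 + 2 = 10 | started |
| 1 | 0 | 4 + 2 = 6 | acute regimen continued |
| 1 | 1 | 8 + 2 = 10 | dose increased |

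Each row holds one plan. Every treatment indicator is an exact function of F and P:

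- started = P − FP
- increased = FP
- continued = F − FP
- ten-session schedule = P

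**Step 2. Count what can be estimated.** Take a candidate factor X.

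- The stratum model has 1, F, P and FP (4 columns) and X times each of these (4 columns): 8 columns, rank 8.
- Add the three drug indicators and X times each: 4 + 4 + 3 + 3 = 14 columns. The rank is still 8.

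The six added columns contribute nothing. An X-by-treatment coefficient and a difference in the prognostic slope of X between strata are the same quantity in these data. They could be separated only by assuming that X has the same prognostic slope in every stratum, and the plan makes no such assumption.

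**Step 3. Look for variation inside a row.** The one discretionary step in the section 5.2 regimen is the week-6 dose step for adolescents who started fluoxetine, and it depends on lack of response. Section 8.4 also allows the drug to be reduced or withdrawn for side effects. Both follow events after entry, so neither gives an unconfounded contrast.

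**Step 4. Show the consequence by simulation.** Assumptions: continuous outcome with unit residual SD; standard normal X; true treatment moderation zero; prognostic slope of X larger by 0.5 SD in partial responders; two-sided 5% test of X × P; 4,000 simulated trials per setting.

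| N | Partial responders (assumed) | Mean X × P coefficient | Significant |
|---|---|---|---|
| 30 | 30% | 0.51 | 21% |
| 30 | 50% | 0.50 | 23% |
| 300 | 30% | 0.50 | 97% |
| 300 | 50% | 0.50 | 99% |

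With the slope difference set to zero, the test rejected in about 5% of trials. So the test works as a test of differing slopes, but it cannot say why the slopes differ. A larger sample makes the misreading more certain.

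**Step 5. Precision, as a secondary matter.** With unit SDs, the detectable slope difference at 80% power is (1.96 + 0.84) × √(1/n₁ + 1/n₂):

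- 15 and 15: 2.80 × 0.365 = 1.02 SD per SD
- 9 and 21: 2.80 × 0.398 = 1.12
- 6 and 24: 2.80 × 0.456 = 1.28

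Even as a description of differing slopes, the interaction would be very imprecise at N=30.

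**The case against.** The best defence is that the plan claims little. It will ask whether factors predict or moderate, carries forward only potential moderators, labels the work hypothesis-generating, disclaims efficacy, and sends the refined strategy on to be tested. All of that is in the text, and it lowers the severity. It does not make the quantity identifiable. The label excuses imprecision and multiple looks, but an exploratory estimate must still bear on the hypothesis it is meant to generate.

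A second defence is that *moderate* may not refer to continuation treatment. The main analyses for Hypotheses 5 and 6 cover acute and continuation treatment together. Adolescents arrive after 12 sessions of IPT-A, 16 sessions, or 12 plus fluoxetine (section 4.3), and the Study Summary mentions early and late decision point groups. Section 1.1 says that acute treatment could be augmented for insufficient response, but not how the augmentation was chosen. If that choice was randomised, an acute-phase contrast might support moderation. This stands, with the reservation that the present cohort is selected on acute response. The rank result concerns continuation treatment only.

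Three stronger readings are tempting and are not supported:

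- A reader might infer that the whole exploratory analysis is invalid. The prediction half is estimable.
- A reader might size the problem by the number of factors tested or by events per factor. No significance rule, binary outcome or model is specified for these analyses, and such counts do not measure aliasing.
- A reader might infer that the R01 will be randomised and so settle the matter. The documents describe it only as a later proposal in which the strategy is tested.

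**Conclusion.** The point holds for moderation of the continuation-treatment effect. Under the stated assignment rule that effect is aliased with prognosis that differs by acute treatment and response, and no sample size resolves it. This conclusion rests on the documents' own rules. The simulation percentages rest on an assumed 0.5 SD slope difference and assumed shares of partial responders, and they illustrate the mechanism without forecasting this trial.

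It does not extend to prediction, nor to a possible acute-phase contrast whose allocation the documents leave unstated. Severity is low: the primary outcome in section 3.2 is feasibility and acceptability, and neither that nor the sample size depends on this paragraph. What is at risk is the step from this pilot to the next strategy, where a prognostic factor could be taken for a tailoring variable.

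**What to change.** In the exploratory paragraph of section 7.2:

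1. Delete *or moderate* and *and moderators* as they apply to continuation treatment. If an acute-phase contrast is meant, name it, state how it was allocated in the linked study, and note that this cohort is selected on acute response.
2. Report the listed factors as exploratory prognostic associations, with estimates and 95% confidence intervals.
3. Adjust for week-16 response status (responder or partial responder) and acute treatment (IPT-A alone or with fluoxetine). Four combinations average 30/4 = 7.5 adolescents each, so provide for adjusting for response status only if the groups are too small.
4. State that these associations do not indicate which continuation treatment to assign, and that moderation needs a design with randomised variation within response strata. Do not state that the R01 is such a design unless that is established.

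The cost is wording: no added data, visits or participants. The downside is a more modest exploratory claim.
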